1 ABBREVIATIONS USED IN THE PROTOCOL

Abbreviation	Term
AE	Adverse event
BMI	Body Mass Index
CBT	Cognitive behavioral therapy
CDC	Centers for Disease Control
CPAQ-8	Chronic Pain Acceptance Questionnaire
EHR	Electronic Health Record
GHP	Geisinger Health Plan
GIRB	Geisinger IRB
IPRPs	Interdisciplinary Pain Rehabilitation Programs
IRB	Institutional Review Board
MME	Milligrams of morphine equivalent
MRN	Medical Record Number
NPRS	Numerical Pain Rating Scale
ODI	Oswestry Disability Index
OUD	Opioid Use Disorder
PCS-4	Pain Catastrophizing Scale
PSEQ-10	Pain Self-Efficacy Questionnaire
PDMP	Pennsylvania Prescription Drug Monitoring Program
PROMIS	Patient Reported Outcomes Measurement Information System
SAE	Serious adverse event
SF-12	12-item Short Form Health Survey
SoC	Standard of Care
VR	Virtual Reality

2 ABSTRACT

EaseVRx™, a software-based virtual reality (VR) medical device, is intended to offer users a prescription pain management tool that manages the symptoms associated with chronic pain and reduces or eliminates the risk of opioid dependence. EaseVRx is based on principles of cognitive behavioral therapy, pain psychology, mindfulness-based stress reduction, biofeedback, and distraction therapy commonly used in interdisciplinary pain rehabilitation programs. We will conduct a proof-of-concept randomized, double-blind, placebo-controlled study to assess the feasibility and efficacy of using EaseVRx as an 8-week, VR-based, at-home program among 100 chronic low back pain patients by gathering pilot data on the efficacy of the intervention in decreasing pain, reducing opioid/non-opioid pharmacotherapy, and improving pain-related quality of life. While VR has been tested in academic medical centers and shown to be efficacious in the management of acute pain, this study will investigate the feasibility of VR use at home to manage chronic pain in preparation for a larger efficacy trial.

3 BACKGROUND AND SIGNIFICANCE

3.1 Chronic pain: an epidemic representing a major unmet medical need.

Chronic pain is one of the most common reasons adults seek medical care¹: chronic pain affects between 50 and 116 million Americans, more so than cancer, diabetes, and cardiovascular disease combined¹⁻⁴. Other estimates suggest that up to 40% of American adults suffer from chronic pain, ranging from mild to severe⁵. Pain treatment and management is traditionally based primarily around utilizing pharmacological management tools, which typically involves opioids. Although some non-opioid pharmaceuticals and non-pharmacological therapies are becoming available, there is still significant unmet need for integrative, non-opioid solutions for chronic pain.

Approximately 25 million American adults are living with moderate to severe chronic pain (i.e. pain scoring 4-7 on a Visual Analog Scale and lasting over 3 months) that limits their activities and diminishes their quality of life^{6, 7}. Close to 85% of these patients do not find meaningful relief from current non-opioid treatments (i.e. they do not experience a long-term $\geq 50\%$ reduction in their pain levels)⁸.

Opioids are commonly prescribed for pain treatment and management. These agents can yield both inconsistent and sub-optimal results⁹ and greatly increase the risk of the patient developing an opioid addiction or Opioid Use Disorder (OUD). Data from the U.S. Centers for Disease Control (CDC) revealed that even a single day of opioid therapy can predict up to a 6% increase in the risk of the patient developing a dependency within a year¹⁰.

Opioids have a significant adverse event profile that includes hypotension, respiratory depression or arrest, aspiration, and/or vomiting. Although these risks are manageable, it is imperative to devise pain alternatives that are cost-effective and improve the risk-benefit profile well above the current standard of care. To reduce addiction and provide relief for the millions of chronic pain sufferers, new low-risk, non-opioid pain analgesics are needed.

3.2 appliedVR's answer for chronic pain: EaseVRx

Therapeutic VR has emerged as an effective, non-pharmacological treatment modality for pain⁹. VR users wear a pair of goggles with a close-proximity screen that creates a sensation of being transported into immersive, three-dimensional worlds. One hypothesis for VR's mechanism of action proposes that by stimulating the visual cortex while simultaneously engaging other senses, VR is able to limit the user's processing of pain signals⁹.

The common nature of mobile high-performance computing has now reduced both the size and cost of VR devices, allowing for VR use in everyday settings like the clinic and at home. As an alternative to opioids, VR has been proven to be effective in decreasing pain during severe burn wound bandage changes, IV line placements, and dental interventions⁹.

Unlike opioids, VR has a reduced risk of the user developing a dependency or addiction to the pain management technique. If a patient can utilize VR for pain management, they can either reduce or potentially remove the need for opioid or other pharmacological management

techniques. This sparing of opioid use greatly reduces the risk of the patient developing OUD or addiction.

appliedVR's investigational EaseVRx product for chronic pain is based on principles of cognitive behavioral therapy (CBT), pain psychology, mindfulness-based stress reduction, biofeedback, and distraction therapy commonly used in interdisciplinary pain rehabilitation programs (IPRPs). These programs often include physical and occupational therapy; exercise therapy; cognitive restructuring with an emphasis on promotion of self-management, self-efficacy, resourcefulness, and activity versus passivity, reactivity, dependency, and hopelessness; behavioral treatment (e.g. relaxation, activity pacing); and opioid tapering and management. The reduction of pain after treatment at IPRPs has been reported to be significant in several metanalyses¹²⁻¹⁴, with one meta-analysis¹² reporting that the mean pain reduction for patients treated at IPRPs was 37% with a concomitant significant decrease (63%) in prescription pain treatment. Moreover, one early metanalysis of 42 published studies¹⁵ reported significant reductions in health-care use after treatment at IPRPs.

Access to interdisciplinary chronic pain management programs is seriously lacking in the United States. In 1999, it was estimated that there were over 1000 interdisciplinary pain management programs in the United States¹⁶. This number has dropped dramatically to 150 in 2011¹⁷. Based on the number suffering from chronic pain, this data suggests there is approximately one interdisciplinary program for every 670,000 chronic pain victims in the United States. EaseVRx is a simple, low-risk, non-invasive device with the potential to become a ubiquitous pain management therapy to address the lack of access to interdisciplinary care. In view of the complex nature of chronic pain, treatment often necessitates use of a blend of different approaches with a focus on maximizing symptom relief so that patients are able to lead the highest quality of life possible.

This study will evaluate the degree and duration of analgesic effect on chronic low back pain from use of the EaseVRx device. To control for any potential placebo therapeutic effect that may be experienced merely by donning a VR headset, a sham VR control group is included in the study design. The VR sham product will consist of a void theater, which is defined as a 2D virtual screen in front of the user that displays a variety of video content. The screen will be surrounded by a solid black environment to minimize immersion. The user experience is best described as being inside of a pitch black movie theater. The content displayed in the void theater will be a variety of 2D nature-related content that is not intended to have therapeutic effect. The VR sham user interface and functionality will be designed to mirror the user interface and functionality of the EaseVRx intervention.

4 HYPOTHESIS AND SPECIFIC AIMS

4.1 Primary Aim 1

Compare pain and pain coping skills among the VR sham and the EaseVRx group. *Hypothesis: Chronic low back pain patients randomized to the EaseVRx approach who use the device in accordance with the treatment protocol will have significantly decreased pain scores and improved pain coping skills 4, 8, and 12 weeks after starting the 8-week VR treatment.*

4.2 Secondary Aim 1

Compare physical function as measured by the Oswestry Disability Index (ODI) among the VR sham and EaseVRx group. *Hypothesis: Chronic pain patients randomized to the EaseVRx approach who use the device in accordance with the treatment protocol will have significantly better physical function (i.e. lower ODI scores) 4, 8, and 12 weeks after starting the 8-week VR treatment.*

4.3 Secondary Aim 2

Compare analgesic medication use among the VR sham and EaseVRx group. *Hypothesis: Chronic pain patients randomized to the EaseVRx approach who use the device in accordance with the treatment protocol will have decreased utilization of opioid and non-opioid pharmacotherapy 4, 8, and 12 weeks after starting the 8-week VR treatment.*

4.4 Secondary Aim 3

To assess the feasibility of EaseVRx as a self-administered, home-based approach to chronic pain management, in terms of patient compliance, program retention, patient satisfaction, and safety. *Hypothesis: EaseVRx will be a feasible approach to chronic pain management, with high rates of patient compliance, retention, and satisfaction among chronic pain patients after completing an 8-week course of treatment with EaseVRx.*

4.5 Secondary Aim 4

Compare healthcare cost and utilization among the VR sham and EaseVRx group among patients with Geisinger Health Plan as their primary insurance. *Hypothesis: Chronic pain patients randomized to the EaseVRx approach who use the device in accordance with the treatment protocol will have significantly lower costs and utilization (i.e. office visits, therapy sessions, inpatient/ED admissions) 3 months, 6 months, and 12 months after starting the 8-week VR treatment.*

5 PRELIMINARY DATA

appliedVR has conducted two small-scale feasibility pilots to understand the acceptability, usability, and satisfaction of EaseVRx on various chronic pain conditions. Both studies provided subjects with the use of an 8-session VR intervention at home. The first pilot measured the preliminary EaseVRx program among 45 chronic pain users of various diagnoses. Surveys were administered for 8 days prior to the intervention to establish a baseline measure of pain and quality of life using the PROMIS Global-10. Pain intensity and interference were also measured daily using the Numerical Rating Scale and Department of Defense/Veterans Administration Pain Supplemental Questions. Findings from this pilot showed participants generally experienced reduction in their pain levels over the 8-day-course of use, particularly in the interference of pain with their mood. On average, participants showed a 22% improvement in pain, 24% improvement in stress, 29% improvement in mood, and 25% improvement in sleep quality (over baseline).

A second, targeted quantitative and qualitative study was conducted to assess pain relief and durability, quality of life impact, and engagement of the 8-session VR program among 30 chronic pain patients with a musculoskeletal pain diagnosis (back, spine, neck or joint pain) or rheumatoid arthritis. Outcomes collected included pain intensity via the Numerical Rating Scale, PROMIS Pain Interference Short Form 6b, PROMIS Sleep Disturbance Short Form 4a, and Stanford Expectations of Treatment Survey. Subjects were also given a brief semi-structured interview after completion of the program to understand their satisfaction and challenges with the VR intervention. Subjects who completed six or more modules improved, on average, across every measured Quality of Life metric. On average, users showed 22% reduction in pain intensity over the course of the program.

6 STUDY DESIGN

6.1 Description

This is a single-center, prospective, randomized, double-blind, placebo-controlled study of the appliedVR EaseVRx headset in subjects with chronic lower back pain. A cohort of 126 patients will be recruited from patients currently seeking care for low back pain at Geisinger. We are assuming a 20% dropout or noncompletion rate, so recruiting 126 patients should provide 100 completes. Patients with moderate to severe chronic low back pain who have largely exhausted non-pharmacological approaches to improving pain and who are currently relying primarily on pharmacotherapy for symptom relief will be recruited for the study. These patients are an ideal study population to include as few treatment options remain for these patients due to insufficient understanding of pain origin, failure of conventional pain management approaches, or unsuitability of surgical interventions. Patients will be randomized by computer 1:1 to either the VR sham or EaseVRx group. Providers and patients will be blinded in regard to whether the patient will receive EaseVRx or the VR sham.

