6.2.2 Inclusion Criteria

- Inclusion criteria include:
 - Able and willing to provide written informed consent
 - Ages 18 to 64 years (inclusive)
 - Based on medical history (including available medical records), chronic low back pain must have been present for at least 3 months
 - Completed at least 4 weeks of non-surgical pain management and physical therapy with no apparent benefit
 - Has a mean NPRS pain score that is \geq to 4 (without rounding) over the 7-day screening period

- Subject has a score of 1-3 based on the American Society of Anesthesiologists Physical Status Classification System
- Agrees to comply with all study requirements throughout the entire study period

Exclusion Criteria

- *Exclusions based on potential medical or lifestyle confounders:*
 - Has a body mass index (BMI) > 40 kg/m²
 - Pain related to cancer, fibromyalgia, or disk herniation
 - History of a major psychiatric disorder not controlled with medication or has behavioral factors that would interfere with proper study procedures
 - Is not ambulatory/has significant motor impairment
 - Surgery in the past 3 months
 - Open workers compensation claim
 - Planning to have surgery in the next 3 months
 - Planning to start a new exercise program in the next 3 months
 - Planning to start a new treatment for their pain (e.g. medication, physiotherapy, acupuncture, electrical nerve stimulation) in the next 3 months
- *Exclusions based on potential drug-related cofounders:*
 - Current or recent history (in past year) of substance abuse disorder
 - Currently pregnant/breastfeeding or planning to in the next 3 months
 - Was administered an epidural steroid during the 3 months prior to screening
- *Exclusions based on ability to use EaseVR effectively:*
 - Comorbidities including neurological, psychosocial, sensory, or other disorders that may impact pain perception
 - Diagnosis of epilepsy, dementia, migraines, or other neurological disorders that may prevent VR usage, and/or other medical conditions predisposed to nausea and dizziness
 - Hypersensitivity to flashing lights or motion
 - Claustrophobia
 - Lack of stereoscopic vision
 - Severe hearing impairment
 - Injury to eyes, face, or neck that prevents comfortable VR usage
 - Planning to take a vacation from their home for more than one week in the next 8 weeks

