6.3 Recruitment

The primary and collaborating investigator(s) will identify potential subjects in the Geisinger system who are scheduled for a clinic visit to address their chronic low back pain. These patients will be pre-screened via manual chart review of their electronic health record (EHR) by the research team. Patients meeting the inclusion/exclusion criteria will be called by an IRB-approved study team member (e.g. primary and collaborating physicians, research project coordinator, research assistant) approximately one week prior to their scheduled clinic visit. After hearing a description of the study and completing a short screening assessment, eligible

patients will be asked to report their average lower back pain over the last 24 hours via a Numeric Pain Rating Scale (NPRS) score for 7 days. Each subject will choose how they want to report their daily NPRS scores and will be given the following options: phone calls, texts, or web-based entry via REDCap. They will be instructed to record their scores at the same time each day (\pm 2 hours).

At the end of the 7-day screening period, the study team will assess daily NPRS scores to determine if the subject meets the pain eligibility requirements: (1) subjects must complete at least 5 of 7 daily NPRS scores in the previous 7-day screening period and (2) the overall average NPRS score must remain between 4 and 10 (inclusive) during the screening period. Subjects who are deemed eligible will be approached by a member of the study team during their clinic visit to provide more information about the study and administer informed consent for interested patients.

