6.7 Secondary Endpoints

Secondary outcome measures include:

- Average daily minutes of VR or sham use at during weeks 1-4 and weeks 1-8.
- Number of days VR or sham used.
- Number of days that participants completed all outcome assessments.
- Patient satisfaction score (min 3 – max 12).
- Likelihood of recommending VR treatment to someone else (min 1 – 10 max).
- Number of adverse events related to the study treatment.
- Change from baseline PSEQ-2, PCS-4, CPAQ-8, SF-12 score at 4, 8, and 12 weeks.
- Change from baseline in total ODI score as well as subscale scores at 4, 8, and 12 weeks.
- Average self-reported daily amount of analgesic medication used during weeks 1-4 and weeks 1-8.
- Total milligrams of morphine equivalent doses filled from PDMP database at 3 months, 6 months, and 12 months.
- Total number of office visits, admissions, emergency room visits, and therapy sessions related to the patient's lower back pain at 3 months, 6 months, and 12 months.
- Total cost of care related to patient's lower back pain at 3 months, 6 months, and 12 months.

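### Section 6.1 describes drug-reliant patients but no entry criterion requires analgesic use, and the planned percent change in MME is undefined for anyone with zero baseline opioid use

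*Combined protocol and SAP*

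**What the plan says.** Section 6.1 describes a selected population: moderate to severe chronic low back pain, non-drug approaches largely used up, and patients "who are currently relying primarily on pharmacotherapy for symptom relief will be recruited for the study".

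The criteria that decide entry are in 6.2.2. The line closest to that description is "Completed at least 4 weeks of non-surgical pain management and physical therapy with no apparent benefit". It concerns past care and names no drug. The other inclusion lines cover consent, age, pain duration, pain score, physical status class and compliance. One exclusion bears on medication: "Planning to start a new treatment for their pain (e.g. medication, physiotherapy, acupuncture, electrical nerve stimulation) in the next 3 months".

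Section 6.3 applies the list by chart review: "Patients meeting the inclusion/exclusion criteria will be called by an IRB-approved study team member". It then adds only diary completeness and a pain level: "the overall average NPRS score must remain between 4 and 10 (inclusive) during the screening period".

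Secondary Aim 2 (section 4.3) hypothesises that EaseVRx patients "will have decreased utilization of opioid and non-opioid pharmacotherapy 4, 8, and 12 weeks after starting the 8-week VR treatment". The matching endpoints in 6.7 are total MME filled at 3, 6 and 12 months, and "Average self-reported daily amount of analgesic medication used during weeks 1-4 and weeks 1-8". Neither is limited to baseline users. Section 6.8.1 compares percent change in several scores and in total opioid usage (MME) by ANOVA or Kruskal-Wallis, and lists opioid use and baseline outcome scores among the ANCOVA covariates.

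**The concern.** The description in 6.1 and the list in 6.2.2 do not define the same population. A patient with three months of back pain, a mean score of 4, an unsuccessful course of conservative care and no current analgesic satisfies every listed requirement but is not the patient that 6.1 describes.

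For the pain endpoint this affects only how the enrolled population is described. For Secondary Aim 2 it matters more, because the planned opioid measure is a change relative to baseline. A patient with no opioid use at baseline has no denominator. Unless the plan says otherwise, such patients drop out of the comparison or are handled by a rule chosen after the data are seen. Either way, the analysis set for a stated aim is not fixed in advance.

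**Working it through.** **Step 1. Does any entry rule carry the condition in 6.1?**

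| Place | Requirement | Current analgesic use required? |
|---|---|---|
| 6.1 | Relying mainly on drugs now | Yes, as description |
| 6.2.2 inclusion | Pain for at least 3 months; at least 4 weeks of conservative care and physical therapy without benefit; mean NPRS at least 4 | No |
| 6.2.2 exclusion | No new pain treatment planned within 3 months | No |
| 6.3 | At least 5 of 7 daily scores; mean 4 to 10 | No |

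Nothing elsewhere in the document closes the gap.

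**Step 2. Can the analysis in 6.8.1 be computed for every patient?** Percent change = 100 × (follow-up MME − baseline MME) / baseline MME. With baseline MME = 0 the denominator is zero and the value is undefined.

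| Patient at Day 0 | Fits 6.1? | Passes 6.2.2 and 6.3? | Percent change in MME defined? |
|---|---|---|---|
| Uses opioids | Yes | Can | Yes |
| Relies on non-opioid drugs only | Yes | Can | No |
| Uses no analgesic | No | Can | No |

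The second row shows that aligning 6.2.2 with 6.1 does not by itself repair the MME analysis.

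**Step 3. Is there a power argument?** The only sample-size figure in the plan is 126 recruited for 100 completers at 20% dropout. It reproduces: 100/0.8 = 125, and 126 × 0.8 = 100.8. No effect size, SD or power is given for any endpoint, so what follows is assumed: 100 completers, 50 per arm; MME among users with mean scaled to 1 and coefficient of variation CV; a 25% reduction in users; non-users at zero; two-sided 5%; share of opioid users p. Power is approximately Φ(ncp − 1.96).

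- All patients, unadjusted: ncp = 0.25p / √(4[p·CV² + p(1−p)]/100).
- Users only: ncp = 0.25 / √(4·CV²/(100p)).
- All patients, adjusted for user status: the p(1−p) term goes, so ncp = 0.25p / √(4p·CV²/100) = 0.25 / √(4·CV²/(100p)). This equals the users-only expression, leaving aside a small interaction term.

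For p = 0.5 and CV = 0.8:

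- Unadjusted: 0.125/√(4 × 0.57/100) = 0.125/0.151 = 0.83, power about 13%.
- Users only: 0.25/√(4 × 0.64/50) = 0.25/0.226 = 1.10, power about 20%.
- Adjusted: 0.125/√(4 × 0.32/100) = 0.125/0.113 = 1.10, power about 20%.

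Simulation with gamma-distributed MME and CV 0.8 agrees. Adjusted against users-only power was 14.2% and 14.4% at p = 0.3, 22.3% and 22.4% at p = 0.5, and 29.6% and 29.7% at p = 0.7.

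With every patient a user (p = 1), ncp = 0.25/0.16 = 1.56 at CV 0.8 and 0.25/0.20 = 1.25 at CV 1.0, so power is about 35% and 24%.

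**The case against.** The strongest reply is that the mismatch does little harm. Patients attending clinic for refractory back pain may mostly be on analgesics already; the trial is a proof of concept that claims no power for this aim; and 6.8.1 already lists opioid use and baseline scores as covariates. Much of this stands. The share of non-users is unknown and could be small. Step 3 shows that a covariate for baseline opioid use would recover essentially all that a users-only analysis offers. What the reply does not meet is the percent-change outcome: a covariate cannot supply a value that is undefined. Nor does 6.8.1 say how opioid use is coded, or that the covariate models apply to MME.

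A reader might go further and infer that non-users will enter and dilute the treatment difference in proportion to their share, so that a null result on Aim 2 could be blamed on this gap. The documents do not support that. They permit entry of non-users without showing that it happens. For MME as 6.8.1 analyses it, non-users have no value and so cannot count as zeros. They are not strictly fixed at zero either: 6.5 leaves other pain management unrestricted, the exclusion covers only new treatment planned within 3 months, and MME is followed to 12 months. A null result would also be hard to interpret if every patient were a user.

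**Conclusion.** The concern holds in a limited form. The mismatch between 6.1 and 6.2.2 is a matter of text and rests on no assumption. That percent change in MME is undefined at zero baseline is arithmetic. Its size equals the proportion of enrolled patients without baseline opioid use, which the documents do not give and which includes patients using only non-opioid drugs.

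The primary NPRS endpoint is not touched. The consequence is confined to Secondary Aim 2 and to how the enrolled population is described. No power loss is claimed: the 24% to 35% figures depend on the assumed 25% reduction and CV of 1.0 or 0.8, and serve only to show that power for this aim would be low anyway.

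**What to change.** 1. Reconcile 6.1 and 6.2.2. Either add to the criteria the condition that 6.1 already states, or reword 6.1 to describe the population that the criteria admit.

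2. In 6.8.1, fix the MME analysis by one of two routes. Either make the comparison in patients with opioid use at Day 0, or drop percent change and compare MME in all patients adjusted for baseline opioid use. This is needed whichever option is taken under (1). In both cases report new opioid starts among baseline non-users separately.

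The same sentence should say which record defines opioid use at Day 0, since 6.5 names both the prescription database and self-report. It should also say that status is fixed before randomisation, which is scheduled for the same day. A subset defined before randomisation keeps the randomised comparison valid.

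Cost: one line in 6.1 or 6.2.2 and one or two sentences in 6.8.1. No new data are needed, because analgesic use is already scheduled at Day 0. The users-only route gives a smaller denominator for the MME endpoint. Adding the entry criterion may increase screen failures, by a number that cannot be estimated from the documents.
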